## 7.4 Data collection

R-M EU will develop a formalized CRF for data collection purposes.

Patients' identities will remain confidential and a Patient ID number will be assigned for the purpose of communicating with the reporting HCP.

"Birth defect" will be defined as a major congenital abnormality or syndrome with exclusion for related minor abnormalities, as defined by EUROCAT (EUROCAT, 2009). HCPs will record any infant birth defect(s) on the CRF via free text. This will then be coded in-house using both MedDRA and ICD-10 codes (ICD-10 Chapter XVII: congenital malformations, deformations and chromosomal abnormalities, as recommended by EUROCAT) to enable comparisons and transfer of data between other sources.

## 7.4.1 Outcomes of potential interest

Data for the following outcomes will be collected:

#### Primary outcome:

 Live birth incidence of minor and major congenital birth defects following exposure to Eurartesim™ for the treatment of malaria whilst pregnant.

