## 4. Study objectives

- The primary objective of this study is to assess the live birth incidence of minor and major congenital birth defects following exposure to Eurartesim™ for the treatment of malaria whilst pregnant or in the one (1) month (30 days) prior to conception.
- The secondary objective of this study is to assess maternal, fetal and infant outcomes following exposure to Eurartesim™ for the treatment of malaria whilst pregnant or in the one (1) month (30 days) prior to conception.

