
## 5.4 Sample Size Calculation

Data for this pregnancy Registry will be regularly collected until the sample size required to detect a 2-fold or greater increase relative to the expected background rate of all birth defects and spontaneous abortions is reached. This will provide an adequate sample to ensure understanding of maternal drug safety. The Registry will be closed to new entries once this number of women with validated follow-up information has been reached and in agreement with the EMA; the data will be transferred to another independent Registry, if in acceptance with the other Registry, and according to ethical standards and national legislation at that point in time. These data will then be compared to background rates to see if there has been a significant increase in birth defects or pregnancy loss amongst these patients. A sensitivity analysis will be performed on the data to check other contributing factors.

The following sample size is derived to detect a clinically significant difference (i.e. a >2x increase in the outcome of concern) relative to expected background rates. In Europe, the assumed background risk of all reported birth defects is 23.719 per 1,000 births (EUROCAT, 2009) and the background rate of spontaneous abortion is 85.6 per 1,000 (Tata *et al*, 2005). Thus, assuming 80% power, 0.05 significance level (one-sided) and a loss to follow-up rate of 5%, we would require 376 pregnant women exposed to EurartesimTM in order to be able to detect a 2-fold or greater increase in birth defects and a 1.5-fold or greater incidence in spontaneous abortions with a one-group test. Calculations are based on a normal approximation to a Binomial distribution (equivalent to a chi-square test). Employing a 5% loss to follow-up rate is deemed appropriate as

utilising the services of ProClinica (refer to Section 7.3) to actively follow-up patients via direct patient contact should reduce the degree of loss to follow-up in this Registry.

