#### At end of pregnancy:

- Date of the end of pregnancy.
- Maternal complications since previous visit/contact.
- Maternal mortality.
- Stillbirth (>28 weeks gestation).
- Early neonatal mortality.
- Gestational age at delivery (estimated from the last menstrual period).
- Live births.

- Infant birth weight (adjusted for gestational age).
- Infant major and minor birth defects (primary outcome of interest).
- Serious adverse events (drug related or not) in the mother or the infant since previous visit/contact.
- Exacerbation of pre-existent clinical condition in the mother since previous visit/contact.
- Comorbidities in the mother since previous visit/contact.
- Concomitant medication use in the mother since previous visit/contact.

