# 6 weeks after end of pregnancy / 14 weeks after end of pregnancy / 12 months after end of pregnancy:

After birth, ProClinica will contact the infant's Paediatrician to obtain medical confirmation of events occurring, e.g. birth defects, infant development, neonatal death.

"Birth defect" will be defined as a major congenital abnormality or syndrome with exclusion for related minor abnormalities, as defined by EUROCAT (EUROCAT, 2009). HCPs will record any infant birth defect(s) on the CRF via free text. This will then be coded in-house using both MedDRA and ICD-10 codes (ICD-10 Chapter XVII: congenital malformations, deformations and chromosomal abnormalities, as recommended by EUROCAT) to enable comparisons and transfer of data between other sources.

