## 7.6 Adverse events

## 7.6.1 Definitions

An adverse event (AE) is defined as any untoward medical occurrence in a patient, which does not necessarily have a causal relationship with their treatment. An adverse event can therefore be any unfavourable and unintended sign (including an abnormal laboratory finding), symptom, or disease temporally associated with the use of a medicinal product, whether or not the event is considered causally related to the use of the product.

Such an event can result from use of the drug as stipulated in the labelling, as well as from accidental or intentional overdose, drug abuse, or drug withdrawal. Any worsening of a pre-existing condition or illness is considered an adverse event.

If an adverse event meets any of the following criteria, it is considered a **serious adverse event (SAE):** 

- **Death of Patient:** An event that results in the death of a patient.
- Infant Mortality: Death of child following live birth
- **Life Threatening:** An event that, in the opinion of the HCP, would have resulted in immediate fatality if medical intervention had not been taken. This does not include an event that would have been fatal if it had occurred in a more severe form.

- **Hospitalization:** An event that results in an admission to the hospital for any length of time. This does not include an emergency room visit or admission to an outpatient facility.
- **Prolongation of Hospitalization:** An event that occurs while the study patient is hospitalized and prolongs the patient's hospital stay.
- **Congenital Anomaly:** An anomaly detected at or after birth, or any anomaly that results in fetal loss.
- Persistent or Significant Disability/Incapacity: An event that results in a condition that substantially interferes with the activities of daily living of a study patient. Disability is not intended to include experiences of relatively minor medical significance such as headache, nausea, vomiting, diarrhea, influenza, and accidental trauma (e.g., sprained ankle).

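### The protocol gives two case definitions for its primary outcome, minor plus major defects and major defects only, and does not say which one the 23.719 per 1,000 benchmark matches

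*Protocol*

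**What the plan says.** Four places in the protocol count both minor and major defects:

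- The primary objective, in Sections 2 and 4, is to "assess the live birth incidence of minor and major congenital birth defects following exposure".
- The primary outcome in Section 7.4.1 is "Live birth incidence of minor and major congenital birth defects".
- The data item for the end of pregnancy in Section 5.5 reads "Infant major and minor birth defects (primary outcome of interest").
- The six-week data items in Section 5.5 again list both kinds.

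Two places say otherwise. Sections 5.5.1 and 7.4 both state that a birth defect "will be defined as a major congenital abnormality or syndrome with exclusion for related minor abnormalities, as defined by EUROCAT". Under the same sections, care providers record any defect as free text, and it is coded afterwards to MedDRA and ICD-10 Chapter XVII. No step that sorts major from minor is described.

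The comparator is in Sections 2 and 5.4: "the assumed background risk of all reported birth defects is 23.719 per 1,000 births (EUROCAT, 2009"). Section 5.7 computes 95% confidence intervals around the incidences of birth defects and of spontaneous abortion and uses them to judge whether either exceeds background.

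**The concern.** In a single-arm registry the comparison with background is the whole inference on birth defects, so the numerator and the benchmark must count the same events. Here the numerator is fixed in two incompatible ways. The benchmark carries the same citation as the major-only definition, but its wording points to all defects. A later analysis plan could follow one text only by departing from the other.

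Few cases are involved. About 8.5 background cases are expected, so classifying a handful of infants one way or the other could create or hide a signal.

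**Working it through.** **Texts side by side.** Take an infant with one minor anomaly and nothing else. Under Sections 2, 4, 5.5 and 7.4.1 this infant is a primary case. Under Sections 5.5.1 and 7.4 it is not. The exclusion of related minor abnormalities could be read narrowly, as dropping only those that accompany a major one. Even so, the definition still requires a major abnormality or syndrome.

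**The plan's own figure.** Inputs from Section 5.4: p0 = 0.023719; a 2-fold increase, so p1 = 0.047438; one-sided alpha 0.05; 80% power; 5% loss.

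- Exact binomial at n = 357: P(X ≥ 13 | p0) = 0.086 and P(X ≥ 14 | p0) = 0.048, so the test rejects at 14 or more cases. Power is P(X ≥ 14 | p1) = 0.801, and 357 is the smallest n that reaches 80%.
- 357 / 0.95 = 375.8, which rounds up to the stated 376.
- The normal approximation that Section 5.4 names gives n = [(1.645·√(p0(1−p0)) + 0.842·√(p1(1−p1))) / (p1−p0)]² = 328, or 346 after loss. So 376 matches exact power and not the stated method. That is a side observation.

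I use n = 357. Expected background cases are 357 × 0.023719 = 8.47.

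**Decision thresholds.**

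- Section 5.7 rule, with an exact (Clopper-Pearson) 95% interval: the lower limit is the 2.5% quantile of Beta(k, n−k+1). At k = 15 it is 0.02370, just below p0. At k = 16 it is 0.02583. An increase is therefore declared at 16 or more cases.
- Section 5.4 sizing test (one-sided 5%): 14 or more cases.

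**Case A: minor and major counted, benchmark major-only, no drug effect.** Let m be the prevalence of infants with only minor defects. The documents give no figure, so the range is assumed. The false-increase probability is P(X ≥ k | 357, p0 + m).

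| m (points) | Expected cases | Exact 95% CI (≥ 16) | One-sided test (≥ 14) |
|---|---|---|---|
| 0 (matched) | 8.5 | 1.2% | 4.8% |
| 0.5 | 10.3 | 5.5% | 15% |
| 1.0 | 12.0 | 15% | 32% |
| 2.0 | 15.6 | 50% | 70% |

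One point corresponds to 357 × 0.01 = 3.6 infants.

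**Case B: major only counted, benchmark includes minor.** Suppose 23.719 per 1,000 includes m minor-only cases and the drug truly doubles major defects. The observed rate is 2(p0 − m), compared with p0.

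| m (points) | Observed rate | Apparent ratio | P(≥ 16) | P(≥ 14) |
|---|---|---|---|---|
| 0 (matched) | 4.74% | 2.00 | 63% | 80% |
| 0.5 | 2 × 1.8719% = 3.74% | 1.58 | 27% | 47% |
| 1.0 | 2 × 1.3719% = 2.74% | 1.16 | 4% | 12% |

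Part of the drop in Case B reflects the lower base rate and not the mismatch itself. The apparent ratio shows the mismatch alone.

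**The case against.** The strongest reply is that no bias has been shown. Section 5.4 describes 23.719 as the risk of all reported defects, which on its face fits a minor-plus-major outcome. If both sides count everything, or both count major defects only, there is no distortion. This stands, and it makes every figure above conditional. It does not remove the contradiction between Section 7.4.1 and Section 7.4.

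A reader might go further and infer that the benchmark must be major-only because it shares its citation with the definition, so that a false signal is to be expected. The documents do not support that. The listed reference is a guide to registering and surveying anomalies, and the scope of 23.719 cannot be read from it.

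A reader might also infer that a live-birth outcome necessarily understates risk, because malformed fetuses are lost before birth. Section 5.4 says only births, not live or total births. Against a live-birth benchmark with equal loss fractions, a 2-fold ratio stays 2-fold. Nor is fetal loss ignored: Section 5.7 includes spontaneous abortion in the primary analysis, so the birth-defect comparison is not the registry's only primary conclusion.

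The one-sided 5% test appears only in the sizing, while Section 5.7 uses 95% intervals and states two-sided hypotheses. The interval figures are therefore the ones to quote first. Finally, 357 counts pregnancies. At the protocol's own 85.6 per 1,000 abortion rate they would give about 357 × 0.9144 = 326 live births, so the percentages are indicative.

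**Conclusion.** The point holds as an unresolved contradiction in the primary case definition, together with a benchmark whose scope is not stated. Its effect is conditional and can run in either direction.

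- If minor defects are counted against a major-only figure, the false-increase rate under the exact 95% interval rises from 1.2% to roughly 5.5% to 50% over the assumed 0.5 to 2.0 points.
- If major defects are counted against a figure that includes minor ones, a true doubling looks smaller than it is.
- If the two happen to match, there is no bias, but the protocol does not secure that.

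The figures rest on 357 evaluable pregnancies, an exact interval and an assumed minor-only prevalence. The contradiction itself rests on no assumption. It should be settled before data are classified, because it decides who is a case in the main safety comparison.

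**What to change.** 1. Use one case definition in Sections 2, 4, 5.5, 5.5.1, 7.4 and 7.4.1. A workable choice is major defects by the Section 7.4 definition as the primary endpoint, with minor defects tabulated separately. Describe how the free-text entries are sorted into major and minor.
2. In Sections 2 and 5.4, state whether 23.719 per 1,000 covers major or all defects and live or total births, and cite the prevalence table behind it. Compare live-born cases only with a live-birth figure of the same scope. If the figure changes, rerun the sample size.
3. Optionally, add a count of anomalies in stillbirths, losses and terminations. Section 7.6.1 already makes such an event serious: "An anomaly detected at or after birth, or any anomaly that results in fetal loss". Label this count a lower bound, since Section 6.2 accepts that the status of aborted fetuses may be unknown.

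The cost is protocol wording, one table and a classification step. A major-only count gives fewer primary cases. At the upper assumed value, minor-only infants would be 2.0 / 4.37 = 46% of a combined count. Keeping them in has its own price, even with a matched benchmark: detecting a doubling of major defects alone would need 432 evaluable pregnancies at 1 point, or 533 at 2 points, against 328 (normal approximation, before loss).

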#### Secondary outcomes:

- Maternal complications.
- Maternal mortality (up to 6 weeks post-delivery).
- Spontaneous abortions (≤28 weeks gestation).
- Elective abortions.
- Ectopic pregnancies.
- Stillbirth (>28 weeks gestation).
- Premature deliveries ( $\leq$ 37 completed weeks).
- Early neonatal mortality ( $\leq 7$  days of birth).
- Neonatal mortality ( $\leq 28$  days of birth).
- Gestational age at delivery (estimated from the last menstrual period).
- Low birth weight (adjusted for gestational age).
- Infant development.

## 7.5 Data management processes

A database will be programmed in ORACLE™ to receive the information collected in the registry. This will include automated edit checks. Data entry screens and edit checks will be validated with test data prior to commencing the formal database entry. Concomitant medications will be coded according to the current version of the WHODrug. Medical history and diseases will be coded according to the current version of the Medical Dictionary for Regulatory Activities (MedDRA). A data handling manual including edit check specifications, data entry guide, tracking guide, authorized corrections, coding instructions, and locking procedure will be written as an operational benchmark.

HCPs will be asked to complete the registry at the different time points.

When discrepancies are identified in the registry, the data management group will issue data correction requests. Resolutions to these queries will require re-authorisation of the HCP.

A final validation of the database will be performed and the database locked before statistical analysis is conducted.

## 7.6 Adverse events

## 7.6.1 Definitions

An adverse event (AE) is defined as any untoward medical occurrence in a patient, which does not necessarily have a causal relationship with their treatment. An adverse event can therefore be any unfavourable and unintended sign (including an abnormal laboratory finding), symptom, or disease temporally associated with the use of a medicinal product, whether or not the event is considered causally related to the use of the product.

Such an event can result from use of the drug as stipulated in the labelling, as well as from accidental or intentional overdose, drug abuse, or drug withdrawal. Any worsening of a pre-existing condition or illness is considered an adverse event.

If an adverse event meets any of the following criteria, it is considered a **serious adverse event (SAE):** 

- **Death of Patient:** An event that results in the death of a patient.
- Infant Mortality: Death of child following live birth
- **Life Threatening:** An event that, in the opinion of the HCP, would have resulted in immediate fatality if medical intervention had not been taken. This does not include an event that would have been fatal if it had occurred in a more severe form.

- **Hospitalization:** An event that results in an admission to the hospital for any length of time. This does not include an emergency room visit or admission to an outpatient facility.
- **Prolongation of Hospitalization:** An event that occurs while the study patient is hospitalized and prolongs the patient's hospital stay.
- **Congenital Anomaly:** An anomaly detected at or after birth, or any anomaly that results in fetal loss.
- Persistent or Significant Disability/Incapacity: An event that results in a condition that substantially interferes with the activities of daily living of a study patient. Disability is not intended to include experiences of relatively minor medical significance such as headache, nausea, vomiting, diarrhea, influenza, and accidental trauma (e.g., sprained ankle).
- Important Medical Event Requiring Medical or Surgical Intervention to Prevent Serious Outcome: An important medical event that may not be immediately life-threatening or result in death or hospitalization, but based on medical judgment may jeopardize the patient and may require medical or surgical intervention to prevent any of the outcomes listed above (i.e., death of patient, life-threatening, hospitalisation, prolongation of hospitalisation, congenital anomaly, or persistent or significant disability/incapacity). Examples of such events include allergic bronchospasm requiring intensive treatment in an emergency room or at home, blood dyscrasias or convulsions that do not result in inpatient hospitalization, or the development of drug dependency or drug abuse, misuse, diversion, accidental exposure, and use in opioid naive patients.
- **Spontaneous Abortion:** Miscarriage experienced by study patient.
- **Elective Abortion:** Elective abortion performed on study patient.

The HCP will use the following definitions to rate the severity for any adverse event being collected as an endpoint/datapoint in the study and for all serious adverse events.

- **Mild:** The adverse event is transient and easily tolerated by the patient.
- **Moderate:** The adverse event causes the patient discomfort and interrupts the patient's usual activities.
- **Severe:** The adverse event causes considerable interference with the patient's usual activities and may be incapacitating or life-threatening.

The HCP will use the following definitions for any adverse event being collected as an endpoint/datapoint in the study and for all serious adverse events, to describe the relationship of the adverse event to the use of Eurartesimm:

- Unsuspected not related to use of medication;
- Suspected potentially related to use of medication.

## 7.6.2 Serious Adverse Event Reporting

#### By Registry HCP

In the event of a serious adverse event (as defined in Section 7.6.1), in addition to the data collected on the CRF, the HCP will notify both REGISTRAT-MAPI and Corporate Drug Safety of Sigma-Tau **within 24 hours** of the HCP becoming aware of the event, using the SAE Form provided.

The completed and signed SAE form shall be sent to:

#### By ProClinica and REGISTRAT-MAPI:

In addition to solicited reporting of adverse events, as described in this protocol, spontaneous reporting of a potential adverse drug reaction to a Sigma-Tau product may occur during a contact. These cases are managed in accordance to a standardized reporting procedure and/or according to the project specific Safety Management Plan.

**REGISTRAT-MAPI** personnel and Contact platforms involved in the project will be trained about their obligation of reporting in that matter.

Following a case notification from the contact platform or REGISTRAT-MAPI personnel, REGISTRAT-MAPI Drug Safety Unit will be in charge of reporting to Sigma-Tau Pharmacovigilance according to the study specific Safety Management Plan.

#### By Sigma-Tau:

Sigma-Tau pharmacovigilance will be in charge to report individual cases (spontaneous and solicited safety cases) to the concerned health authorities.

Case processing and expedited and/or periodic reporting modalities will be defined in a Safety Management Plan in accordance with Volume 9A, and particularly, for pregnancy cases, with chapter I.5.4 "Reporting of Outcomes of use of a Medicinal Product During Pregnancy" and related guidances, including, but not limited to, "Guideline on the exposure to medicinal products during pregnancy: need for post-authorisation data".

## 8. Registry timelines

These timelines are based on Eurartesim™ being available on the market by June 2012:

Validation of study documents:	June 2012
Ethics submission:	June 2012
Launch of Eurartesim ™ :	June 2012
First patient in:	July 2012
Recruitment rate analyses:	December 2012, and every 1 year thereafter
Interim statistical analyses:	June 2014, and every 2 years thereafter
Last patient in:	May 2017
Final Clinical Study Report:	September 2019

## 9. Ethics considerations

## 9.1 Ethical Conduct of the Study

The study should be conducted in compliance with the protocol, Good Epidemiology Practice guidelines, the ethical principles arising from the Declaration of Helsinki revised in 1989, and all current local regulations.

Participating HCPs are assured by the initiator of the study that it will be conducted in accordance with the provisions of the above regulations and principles and that it will meet current laws and practices.

The data collected during the study will be obtained from medical notes and information provided by the patients.

The study will not alter the treatment management of the patients and no invasive procedures or special surveillance measures are required by the protocol.

